In this protocol the conditioning phase (one session) will be followed by the extinction phase (one session) during which the CS will be presented repeatedly without the US. Thereafter, the reversal of extinction phase will occur (one session) in which the return of the CR will occur spontaneously, or by reinstatement or by renewal. As a measure of autonomic activation we will record the skin conductance throughout all phases of conditioning by use of a Skin Conductance Coupler (V71-23, Colbourn Instruments, Boston MA).

In summary, under this cognitive protocol separate trials will include sessions of the habituation phase which is involves unpaired presentation of stimuli, the acquisition phase which involves the

Date: February 19, 2023

Principal Investigator: [name].

Application Number: NA\_00079932

paired presentation of stimuli, and extinction of conditioning and reversal of extinction phases. Decreased extinction or increased reversal of extinction may characterize pathologic fear or anxiety traits. Each of these phases may comprise a separate session or trial of the conditioning protocol as described above. Intraoperative studies will involve only attention testing or the conditioning and extinction phases of conditioning protocols.

Some healthy subjects, chronic pain patients, and the patients described above with epilepsy will be involved in attentional and learning protocols as described above. Stimuli are listed above (Objective II: Sensory Processes: Sensory Stimulation) and include laser (item 2), Thermode (item 3) and electric (item 7) in a single train, or two levels of stimulus intensity of one modality in a single train, e.g. low and high levels of the electric modality. Either modality may be nonpainful, or painful with a pain level of less than 6 out of 10 on a scale in which 0 is no pain and 10 is the worst pain imaginable. Often one of the two modalities of stimulation will often be painful while the other is nonpainful. The two modalities or intensities of stimuli will be applied at random interstimulus intervals and in random order, so that one stimulus may be less frequent (e.g. 5 to 25% of total stimuli) than the other (e.g. 95 to 75%). The subject will be asked to count the stimuli or signal the occurrence of one or both stimuli by key presses, which indicate detection of that stimulus.

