**Risks for Research Testing Procedures for both Intra- and Extra-operative Sessions:**

Somatic sensory research testing:

Sensory stimuli, such as the laser, mechanical, nonpainful electrical stimulation, and ice water (see above section on '*Research Testing Procedures ...*'), are applied so that the patient can remove themselves from the stimulus at any time. In addition, the thermal stimulators (laser and contact thermode) are computer controlled, with built in controls to prevent injury. The laser stimuli may lead to a grade 1 burn (sunburn) manifest by skin freckling lasting for a few days.

The ischemia test lasts for about three minutes. In the ischemia test, the investigator will stand at the patient's side and will be prepared to deflate the cuff at any time.

Biological Specimen Sampling:

There is a low risk of infection or bruising from the blood sampling. We reduce this risk by using sterile needles, alcohol scrub, applying pressure to your arm after removing the needle, and using state certified phlebotomists experienced in conducting blood draws. An additional low risk possibility is that a participant might experience light-headedness associated with the needle stick.

There are no known risks to providing a saliva sample.

Motor Research Testing:

During Torque motor testing the patient will be able to release the manipulandum of the Torque Motor at any time. Unexpected movements of the torque motor will be aborted by an accessible switch which will disable the machine and which may be pushed by anyone in the room.

Psychological Research Testing:

These are minimal risk procedures. In conditioning studies, the CR will be extinguished by presenting the CS+ without the US (extinction) to normalize the CR. Numerous imaging studies of classical aversive conditioning and psychological interviews and questionnaires have been carried out safely at universities across the United States in psychiatric patients and in healthy controls (reviewed in (Rauch et al., 2006; Phelps, 2006)).

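### In extra-operative aversive conditioning that includes the reversal phase, the risk text says extinction normalises the conditioned response, but the next phase is meant to bring it back and no re-extinction or check is stated

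*Combined protocol and SAP*

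**What the plan says.** Two places bear on this point.

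- **Section 8, Risks, Psychological Research Testing.** The procedures are described as minimal risk. For conditioning studies the text then says that "the CR will be extinguished by presenting the CS+ without the US", and gives the purpose as normalising the CR. The governing heading is "Risks for Research Testing Procedures for both Intra- and Extra-operative Sessions", so the statement covers work both inside and outside the operating room. Reversal of extinction is not mentioned.
- **Section 4, Objective III: Sensory Processes: Behavioral Tasks.** Here "the conditioning phase (one session) will be followed by the extinction phase (one session) during which the CS will be presented repeatedly without the US". After that, "the reversal of extinction phase will occur (one session) in which the return of the CR will occur spontaneously", or through reinstatement or renewal. The summary of the cognitive protocol gives habituation, then acquisition, and ends with "extinction of conditioning and reversal of extinction phases". It adds that a phase may be its own session or a trial. Intra-operative work is limited to attention testing or to conditioning and extinction.

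The same part of Section 4 says that extra-operative conditioning may take two or three sessions on different days. It allows either an aversive unconditioned stimulus (US: painful laser, thermode or electrical) or a one-dollar reward. Skin conductance is to be recorded in every conditioning phase.

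**The concern.** Someone who reads only Section 8 would conclude that a participant given aversive conditioning has the learned response extinguished and is back to normal when the procedure is over. Section 4 describes a longer procedure. In the full extra-operative sequence, extinction is the second-to-last phase, and the last one exists to make the CR return. The risk section thus describes a shorter procedure than the one planned, and its assurance rests on a step that the next phase is designed to undo.

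What is at stake is the accuracy of the risk description and the handling of participants at the end of the sequence. No estimate is at stake. The protocol itself expects the return to vary between people: "Decreased extinction or increased reversal of extinction may characterize pathologic fear or anxiety traits". The participants in whom the return would be largest are therefore those for whom the normalisation statement fits least well.

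**Working it through.** No arithmetic applies beyond counting sessions. The plan gives no figure to reproduce, so the check sets the sections side by side.

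1. **What Section 8 asserts.** Measure: CS+ presented without the US. Purpose: normalise the CR. Scope: conditioning studies, in intra- and extra-operative sessions alike.

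2. **Order of phases in Section 4, Objective III.**
   - Extra-operative, full sequence: habituation, acquisition, extinction, reversal of extinction (CR returns).
   - Intra-operative: conditioning, extinction. No reversal.

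3. **Is anything stated after reversal?** The narrative stops at reversal, and the summary lists reversal last. Section 8, Steps taken to minimize the risks, has items on sensory tests, the ischemia test, motor testing, tDCS, the speech task and cortical stimulation, but none on conditioning. No section states a second extinction, or a criterion for the CR having fallen before the participant leaves.

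4. **Where the two sections agree and where they do not.**

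| Conditioning schedule | Last phase described | Consistent with Section 8? |
|---|---|---|
| Intra-operative | Extinction | Yes |
| Extra-operative, stopping at extinction | Extinction | Yes |
| Extra-operative, with reversal, aversive US | Reversal | No |
| Extra-operative, with reversal, reward US | Reversal | Not in wording, but a returned CR raises no comparable concern |

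5. **How many sessions?** At one session each, conditioning, extinction and reversal make 1 + 1 + 1 = 3 sessions. Section 4 allows two or three. A two-session schedule could omit reversal, or could combine phases, since a phase may be a trial within a session. The text does not say which, so the share of extra-operative participants who reach reversal cannot be worked out.

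6. **What else protects the participant?** Withdrawal is allowed at any time (opening of Section 8). Sensory stimuli are applied so that patients can remove themselves, and the thermal stimulators have built-in controls (Section 8, somatic sensory testing). Painful stimuli in these tasks are held below 6 out of 10 (Section 4, Objective III). These limit exposure to the stimulus. None is directed at a CR that persists after the session.

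**The case against.** The best reply is that Section 8 promises extinction and Section 4 schedules it. Nothing in Section 8 says that extinction comes last or that the CR is absent when the participant leaves. Measuring a returned CR also means presenting the CS. If those presentations are unreinforced, they already meet Section 8's own description of extinction, and the response may decline within the reversal session. Section 8 also cites earlier safe use of aversive conditioning in psychiatric patients and healthy controls.

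Part of this stands. Extinction is carried out, so a reader who infers that the safeguard is simply not delivered goes too far. The state of the CR at exit is inferred from the order of the phases. The protocol does not give the number of reversal trials, whether they are reinforced, or how the session ends. What does not stand is the claim that the sections agree. A stated purpose of normalising the CR is not met by a sequence whose last described phase aims at its return, unless something further is said, and nothing is.

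Three stronger readings are tempting but not supported:

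- *That the whole protocol ends on reversal.* Intra-operative conditioning explicitly does not, and a two-session extra-operative schedule may not.
- *That extinction is the only protection.* It is the only stated measure aimed at the CR. The general protections listed above also apply.
- *That patients with PTSD are sent home with a restored fear response.* Chronic pain with comorbid PTSD is a study population, but only some chronic pain patients enter the learning protocols. The visit schedule gives that group one testing visit of about two hours. Phases may be trials within a session, so exposure to reversal is possible, but nothing shows that it occurs.

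**Conclusion.** The point holds in a narrow form. For extra-operative aversive conditioning that includes reversal, Section 8 presents extinction as the step that normalises the CR, while Section 4 follows it with a phase intended to restore the CR and states no re-extinction or check. Schedules that end at extinction are not affected.

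The conclusion assumes that the phases run in the order written and that nothing further is done after reversal. If the reversal session in practice ends with enough unreinforced presentations, only the wording is at fault.

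The size of any harm cannot be judged from the documents, which give no rate, severity or duration for a returned CR. It is probably small. No outcome, sample size or analysis depends on it. This is a minor correction worth making.

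**What to change.** Reconcile Section 4 (Objective III) with Section 8 (Psychological Research Testing). Either route removes the contradiction, and the choice belongs to the investigator and the IRB.

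- **Change the procedure.** End the reversal session with unreinforced CS+ presentations after the last measured trial, and use the skin conductance already being recorded to see whether the response has fallen. This costs a few minutes of one session. Because it follows the last measured trial, it leaves the outcome data untouched.
- **Change the risk text.** State in Section 8 that some extra-operative participants go on to a phase in which the CR is expected to return, and drop the normalisation statement for that sequence. This costs only the rewording.

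Whichever is chosen, Section 4 should say which phases a two-session schedule contains, so that it is clear who reaches reversal.

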### **Transcranial Direct Current Stimulation (tDCS) Device**

Date: February 19, 2023

Principal Investigator: [name].

Application Number: NA\_00079932

We employ surface electrodes (TransQE from IOMED®, surface area: 25 cm^2) connected to a conventional tDCS device Phoresor® II Auto (Model No. PM850, IOMED®, Salt Lake City, Utah 84120, USA) to deliver DC current to the scalp via surface electrodes.

tDCS will be administered with a current strength of 2 mA for maximum of 10 min by a constant current stimulator. Based on subject restrictions two types of electrode configuration will be applied:

1. Conventional rectangular sponge pad: we will use a pair of saline-soaked surface sponge electrodes (anode: 7 × 5 cm^2; cathode: 7 × 5 cm^2). The anode electrode will be positioned over the motor cortex representational area of the hand region on an affected side, and the return electrode will be placed above the contralateral motor cortex area.

2. 4 × 1 ring: The central active electrode will be placed above the representational area of the unaffected side hand (coinciding with the center of the anodal pad used for regular-pad stimulation) and surrounded by four return electrodes (each at a ring center to ring center distance of 3.5 cm from the active electrode) which will be connected to a four-to-one wire adaptor for the DC stimulator. Altogether five sintered Ag/AgCl ring electrodes (outer radius: 12 mm, inner radius: 6 mm) will be stabilized with plastic holders filled with EEG conducting gel (H + H Medical Devices, Germany and with gel-skin contact area ~25 ± 2.5 mm^2). Since the sensation to tDCS could differ with electrode and gel type (Minhas P, et al. 2010), here we will apply the suggested Ag/AgCl sintered ring electrodes (Minhas P, et al. 2010), and the conducting gel for less skin sensation as reported by the subjects.

Numerous methods utilize external landmarks to locate the motor strip (pre central gyrus). The motor strip typically lies anywhere from 4 to 5.4 cm behind the coronal suture. Based on the International 10/20 EEG system the C3 and C4 locations correspond to the left and right motor cortex (Edwards et al., 2013; Kido et al., 1980; Sarmento et al., 2008; Ebeling et al., 1987).

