Nitsche et al. have studied several hundred subjects so far without reporting any side effects apart from a slight itching under the electrode and a short phosphene if the stimulation was switched on or off abruptly. In his own work and in his review of the modern literature, Priori found no evidence or mention of adverse effects using this technique. Additionally, several months' use of this technique at NIH in approximately 30 subjects (Drs. [name] and [name]) was performed in the absence of any deleterious side effects. All of these reports are in accordance with our experiences in a recently performed study by [name] in elderly healthy volunteers and chronic stroke patients. Furthermore, the NINDS IRB approved recently a protocol of Drs [name] and [name] (03-N-0116) to apply tDCS repetitively (8 sessions) in Parkinson patients. Both anodal and cathodal tDCS have been successfully applied during 20 minutes in 12 stroke patients, including 2 patients with cortical stroke, without any adverse effects

Finally, a review paper discussed the safety of tDCS in humans. tDCS application over motor and non-cortical areas in 102 subjects (in healthy individuals, migraine patients, post-stroke patients, and tinnitus patients) revealed the most common adverse effect after tDCS was a mild tingling sensation, followed by fatigue, then a light itching sensation under the stimulation electrodes. Not as common, but mentioned, were headache, nausea, and insomnia. Poreisz et al. concluded that tDCS is associated with very minor adverse effects in healthy humans and patients with varying neurological disorders

In addition, other recent publications have shown that it is also possible to use 2mA intensities without significant risk or complications (current density of 0.095 mA/cm^2 and delivered a total charge of 0.086 C/cm^2.) over the cerebellum or prefrontal cortex for 15 minutes without any

Date: February 19, 2023

Principal Investigator: [name].

Application Number: NA\_00079932

complications. Finally, in an editorial by Bikson, unpublished data is reported using current densities of 25.46 A/m^2 for 20 minutes with minimal sensation and no skin damage.

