An animal study (rat) (Liebetanz et al., 2009), investigated the safety limits of extended transcranial direct current stimulation. Fifty-eight rats received single cathodal stimulation at 1–1000  $\mu$ A for up to 270 min through an epicranial electrode. Histological evaluation was performed 48 h later. A threshold estimate was calculated from volumes of DC-induced lesions. Brain lesions occurred at a current density of 142.9 A/m^2 for durations greater than 10 min. For current densities between 142.9 and 285.7 A/m^2, lesion size increased linearly with charge density; with a calculated zero lesion size intercept of 52400 C/m^2. Brains stimulated below either this current density or charge density threshold, including stimulations over five consecutive days, appeared the same as nonstimulated controls. The results of these systematic animal studies provide an estimate of a safety threshold for deleterious DC effects. With respect to the charge density, the upper limit used for these proposed human intraoperative studies is lower by two orders of magnitude.

One perceived limitation for the use of tDCS intraoperatively in subjects undergoing DBS lead placement is the resulting modification of current flow by the presence of surgical burr holes. Modeling studies can provide insight into how skull defects would affect current flow through the brain. Based on modeling results modifying the stimulation current intensity and changing the electrode location or electrode type can compensate for the effects (Datta et al., 2010). In the case of a craniotomy, there is a relatively highly conductive fluid pathway for current entering the brain, but it is highly dependent on the craniotomy position relative to the electrode montage used with tDCS. A small defect under the anode electrode leads to current flow in the cortex restricted to locations directly under the defect. A similar sized defect placed between the electrodes does not significantly alter current the flow pattern in comparison with a healthy head with no defect ( Datta et al., 2010).

The tDCS electrodes in this study will be placed at least 3 cm from the closest burr hole.

The psychological and neuropsychological tests are administered by pencil and paper or by a structured interview with a practicing psychiatrist or clinical psychologist.

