#### **a. Steps taken to minimize the risks.**

- i) Risks related to computer-controlled sensory tests (laser and contact thermode) are controlled by software limits, and by limitation of the power delivered by any stimulator. With these tests (number 1 above section 'Medical risks listing ...') and with the ice water test, the patient will have the ability to remove his hand from the water at any time.
- ii) Risks related to the ischemia test (number 2 above) will be minimized by having the investigator at the patients side throughout the test, prepared to deflate the cuff at any time.
- iii) The risks of motor testing (number 3 above) are controlled by limits of the torque motor excursion and by the patients' ability to release the manipulandum at any time; any member of the research team will be able to disable the stimulator if they observe unexpected movements of the motor. All subjects will have the option to withdraw from any protocol without penalty.
- iv) For the tDCS system, we will use either Conventional rectangular sponge pad: we will use a pair of saline-soaked surface sponge electrodes (anode:  $7 \times 5 \text{ cm}^2$ ; cathode:  $7 \times 5 \text{ cm}^2$ ). The anode electrode will be positioned over the motor cortex representational area of the hand region on an affected side, and the return electrode will be placed above the contralateral motor cortex area or  $4 \times 1$  Ag/AgCl ring electrodes: with plastic holders filled with EEG conducting gel. This will reduce the total applied current and increase the stability of stimulation. The  $4 \times 1$  ring configuration will increase the flexibility of electrode placement with respect to the burr holes and also will allow focal stimulation of the motor cortex ( Datta et al., 2010). This allows for a very low intensity current stimulation level. Even in the worst case, the current density generated by transcranial direct current stimulation on healthy head with a two electrode montage ( two  $5 \times 5 \text{ cm}$

Date: February 19, 2023

Principal Investigator: [name].

Application Number: NA\_00079932

electrode pads) using 2 mA on the bilateral primary motor cortex ( C3 anodal an C4 cathodal), is about  $0.95 \text{ A/m}^2$  which is far below the tissue damage threshold . Brain tissue damage generally occurs at a current density of  $142.9 \text{ A/m}^2$  or greater (Liebetanz et al., 2009).

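### The roughly 100-fold charge-density safety margin for intraoperative tDCS holds for the pads but not for the permitted 4 × 1 ring, where it is about 15-fold or 1.1-fold

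*Combined protocol and SAP*

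**What the plan says.** **The margin.** Section 8, under transcranial direct current stimulation, describes a rat study. Lesions occurred at 142.9 A/m² for durations above 10 minutes, and the extrapolated zero-lesion charge density was 52,400 C/m². On findings below these levels it says: "Brains stimulated below either this current density or charge density threshold, including stimulations over five consecutive days, appeared the same as nonstimulated controls". It then states the margin for this study: "With respect to the charge density, the upper limit used for these proposed human intraoperative studies is lower by two orders of magnitude".

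**The settings.** Section 6, under the tDCS device, gives one setting: "tDCS will be administered with a current strength of 2 mA for maximum of 10 min by a constant current stimulator". It continues: "Based on subject restrictions two types of electrode configuration will be applied". The first configuration is a pair of 7 × 5 cm sponge pads. The second is a 4 × 1 ring with one central active electrode and four returns. The ring hardware is described as "Altogether five sintered Ag/AgCl ring electrodes (outer radius: 12 mm, inner radius: 6 mm", with a "gel-skin contact area ~25 ± 2.5 mm" (the unit is square millimetres). Section 4, item 8 also describes 25 cm² surface electrodes, used intraoperatively at 2 mA for 10 minutes.

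**The risk-minimisation text.** Section 8a, item iv presents the ring as making it easier to place electrodes around the burr holes. It says the current will be lower but gives no figure. Its limiting case is for large pads only: "Even in the worst case, the current density generated by transcranial direct current stimulation on healthy head with a two electrode montage", with two 5 × 5 cm pads at 2 mA and about 0.95 A/m².

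**Human exposure cited.** Section 8 also mentions an editorial in which "unpublished data is reported using current densities of 25.46 A/m"² for 20 minutes.

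**The concern.** An upper limit for the intraoperative studies has to cover the least favourable configuration that the protocol allows. The ring's electrodes are far smaller than the pads, and charge density rises in inverse proportion to area. A margin that fits the pads therefore cannot be carried over to the ring at the same current and duration. No charge density for the ring appears anywhere in the protocol.

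This is the protocol's quantitative charge-density assurance to the reviewing board, for research-only stimulation of awake surgical patients with open burr holes. If it is wrong for one permitted montage, the board has approved that montage on a figure that does not describe it.

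**Working it through.** **Inputs**

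- Current I = 2 mA and time t = 600 s (Section 6; also the intraoperative paragraph of Section 4, item 8). Charge = 0.002 × 600 = 1.2 C.
- Charge-density threshold 52,400 C/m² and current-density threshold 142.9 A/m² (Section 8).
- Areas: 25 cm² electrode (Section 4, item 8); 7 × 5 = 35 cm² pad (Section 6); ring contact area 25 mm², range 22.5 to 27.5 mm² (Section 6); ring annulus from the stated radii, π(12² − 6²) = 339.3 mm².
- Assumption: the ring's one active electrode carries the full 2 mA.

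**Formulas**

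Current density j = I / A. Charge density q = j × t. Margin = 52,400 / q.

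**Results at 2 mA for 10 minutes**

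| Electrode | Area | j (A/m²) | q (C/m²) | Margin |
|---|---|---|---|---|
| Sponge pad | 35 cm² | 0.57 | 343 | 153 |
| Surface electrode | 25 cm² | 0.80 | 480 | 109 |
| Ring, full 12 mm disc | 452.4 mm² | 4.42 | 2,653 | 19.8 |
| Ring, annulus from radii | 339.3 mm² | 5.89 | 3,537 | 14.8 |
| Ring, contact area, upper | 27.5 mm² | 72.7 | 43,636 | 1.20 |
| Ring, contact area, stated | 25 mm² | 80.0 | 48,000 | 1.09 |
| Ring, contact area, lower | 22.5 mm² | 88.9 | 53,333 | 0.98 |

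The first two rows reproduce the protocol's claim, so charge over electrode area is evidently its basis. Every ring row falls short. The two stated descriptions of the ring differ by 339.3 / 25 = 13.6-fold.

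**What would restore 100-fold**

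- Area needed at 2 mA for 10 minutes: 1.2 / 524 = 0.00229 m² = 22.9 cm².
- Ring current needed for 10 minutes, 524 × A / 600: 0.022 mA at 25 mm², or 0.30 mA at 339.3 mm².
- The lowest human tDCS current named is 1 mA (Section 3 and the human safety data in Section 8). Halving the current doubles the margin, to 2.2-fold at 25 mm² or 29.6-fold at 339.3 mm².

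**Against the cited human exposure**

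25.46 A/m² × 1,200 s = 30,552 C/m².

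- At 25 mm² the ring is at 80 / 25.46 = 3.1 times that current density and 48,000 / 30,552 = 1.6 times that charge density.
- At 339.3 mm² it is well inside on both (5.89 A/m² and 3,537 C/m²).

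**Against the current-density threshold**

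80 / 142.9 = 56% at 25 mm², and 88.9 / 142.9 = 62% at 22.5 mm².

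**Duration**

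Section 4, item 8 also gives 20 minutes, in its general paragraph on 25 cm² electrodes. That would give 960 C/m² and a margin of 55-fold for that electrode. The protocol nowhere gives the ring 20 minutes.

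**The case against.** - **The claim is right for the intraoperative procedure that is spelled out.** The only step-by-step intraoperative description, in Section 4, item 8, uses 25 cm² electrodes for 10 minutes, which gives 109-fold. The limiting case in Section 8a gives 0.95 × 600 = 570 C/m², or 92-fold. On this view the sentence omits a montage but contains no miscalculation. That is fair as a description, but the sentence is not restricted to those electrodes, and Section 8a ties the ring to burr-hole placement, which is a surgical reason.
- **The 1.1-fold figure rests on a doubtful area.** A contact area of 25 mm² is hard to square with a 12 mm outer radius, and it may be a slip. This stands, and 1.1-fold should be read as conditional. The conclusion does not depend on it, because the larger area also fails.
- **Two orders of magnitude is a rounded phrase.** On a log scale, anything above about 32-fold (10^1.5) could round to it. On that reading the 55-fold figure for 20 minutes still fits, and the annulus would need about 0.94 mA (2 × 14.8 / 31.6) instead of 0.30 mA. At 1 mA the annulus is borderline at 29.6-fold, and a full disc passes at 39.5-fold. At 2 mA, the only current documented for the ring, neither 14.8-fold nor 1.09-fold fits even this loose reading.
- **The current will be lower for the ring.** Section 8a says so without a value, so 2 mA is an upper bound, and it remains the only device setting given.
- **No harm is shown, and tDCS is a secondary part of an exploratory study.** This is true and bears on urgency. It does not make the stated margin correct.

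**Conclusion.** The concern holds. At 2 mA for 10 minutes the stated margin is right for the pads (109- to 153-fold) and wrong for the ring: 14.8-fold on the stated radii, or 1.09-fold on the stated contact area (0.98 to 1.20 over its tolerance). Measured against 100-fold, the sentence overstates the ring's margin by a factor of about 7 (100 / 14.8) to 92 (100 / 1.09).

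This rests on two assumptions. The central ring electrode is taken to carry the full 2 mA. Density at the electrode surface is compared directly with the animal threshold, as the protocol's own pad comparison appears to do; scalp and skull attenuation is not modelled.

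This is an unsupported margin and not a predicted lesion. On every stated area the ring is below 142.9 A/m², and the protocol reports normal brains below either threshold. The unresolved area does matter in practice, because it decides whether the ring lies inside or outside the highest-density human exposure that the protocol cites. The conflicting 20-minute duration is a lesser point. It sits under a heading that covers both intra- and extra-operative sessions, so it needs to be settled too.

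**What to change.** 1. Reconcile the ring's contact area with its radii, and state the current to be used with the ring.
2. Give one tDCS duration for each setting, and remove the conflict between 10 and 20 minutes.
3. Replace the margin sentence in Section 8 and the limiting-case sentence in Section 8a, item iv with a short table. It should show current density, charge density and margin for each permitted montage and duration. Quote the least favourable row, and keep the statement that no lesions were seen below either threshold.
4. If the ring will not be used intraoperatively, say so and limit the margin sentence to the pads.

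The cost is a recalculation and amended device and risk text, with no new data. The stated margin for the ring will look less favourable. No particular dose is proposed here.
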